Specific Aim 1: To measure the effects of respiratory training on respiratory and voice outcomes in patients with presbyphonia. Hypothesis 1: The respiratory training groups (inspiratory and/or expiratory) will demonstrate greater improvement in respiratory outcomes, measured through pulmonary function tests and respiratory pressure measures, compared with the voice exercises-only group. Hypothesis 2: The respiratory training groups (inspiratory and/or expiratory) will demonstrate greater improvement in voice-related outcomes than the voice exercises-only group.

Secondary Aim 1: To assess the reliability of the ratings for subjective outcomes (videostroboscopy ratings and perceptual judgements of voice quality). Hypothesis 1: Intra-judge reliability will be of at least 80%. Hypothesis 2: Inter-judge reliability will be of at least 70%.

Specific Aim 2: To determine how baseline measures of respiratory function influence the effects of respiratory training (respiratory and voice outcomes). Hypothesis 1: inspiratory training will have maximal effect on patients with decreased maximum inspiratory pressure (MIP). Hypothesis 2: Expiratory will have maximal effect on patients with decreased maximum expiratory pressure (MEP).

This is an initial feasibility and mechanistic study that has the potential to reveal that respiratory training can significantly improve outcomes from voice therapy by acting in synergy with voice exercises. Currently,

much time is spent in voice therapy on subthreshold 'breathing exercises' that lack evidence. This project will provide guidance for evidence-based and theory driven approaches to leverage respiratory function to improve voice therapy. Conversely, negative findings from this study would indicate that respiratory function is ineffective and not a viable target for therapy in this patient population.

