- Acoustic assessment: The microphone is positioned at a 45° angle and at a standardized distance from the mouth of the participant. The participant is asked to sustain phonation on the vowels /a/ and /i/ at a comfortable loudness for 3-5 seconds and as low and as loud as possible, to glide to a high pitch and to a low pitch, and from a soft voice to a loud voice. They are asked to sustain the vowel /a/ for as long as possible. They are then asked to read the 6 CAPE-V sentences and to have a short natural conversation with the speech therapist. The participant is then asked to rate their perceived phonatory effort (PPE) on a scale.
- Self-Assessment questionnaire: the participant will be asked to fill out the Communicative
 Participation Item bank (CPIB) questionnaire, which consists of 10 questions on communication.

Participants will be stratified based on their muscle pressure measures: 1) within normal limits MIP and MEP; 2) preserved MIP and decreased MIP; 3) preserved MEP and decreased MIP; 4) decreased MIP and MEP. This stratification is crucial to the study design because it will ensure an equal repartition of the

different respiratory profiles and deficits across treatment groups. Participants that don't meet stratification requirements will be excluded from the study.

Participants will be blocked-randomized into three groups (allocation ratio 1:1:1): IMST, EMST and VFE (see description of the interventions below).

Experimental Interventions (Procedures to be performed solely as part of this research study):

Participants in all groups will attend four sessions with a study team member. Intervention sessions will last approximately 30-45 minutes each. Each session will include pre- and post-treatment muscle pressure and acoustic measurements.

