
Sample Size Justification

We considered maximum phonation time (MPT) as the primary outcome measure for sample size calculation. This measure was chosen because 1) low MPT is a hallmark of patients with presbyphonia, and 2) MPT is directly affected by both the laryngeal and respiratory systems. To estimate the expected effect size between VFE and the I+IVFE and E+VFE groups, we considered MPT values from groups of an

elderly population with different glottal closure and spirometry profiles (49). Considering that a combined intervention (inspiratory or expiratory training combined with voice therapy) would address both laryngeal and respiratory deficits, and that a voice therapy-only intervention would directly address only the laryngeal deficits, we compared MPT between the no-deficit group (complete glottal closure and normal spirometry) and the respiratory-deficit group (complete glottal closure and altered spirometry)(49). Based on these values and the pooled standard deviations, the expected difference between our control and experimental groups would represent a large effect size. As for the withinsubjects effect, a study by Nam et al.(50) found a 33% increase in MPT following a respiratory training intervention program in young adult singers. This corresponds to a very large within-subjects effect size with values of d exceeding 1.2. For Aim 2, we will assess improvement in 2 ways: function (a MPT increase of 4 seconds, which has been associated with a positive perceived effect following voice therapy in older adults(51)) and patient perception of function (a Glottal Function Index (GFI) score decrease of 4 points). An increase of 4 seconds in MPT and a decrease of 4 points on the GFI instrument both correspond to medium-large effect sizes considering the reported standard deviations of these measures in older subjects and in patients with glottal insufficiency (5.1 and 4.5, respectively) (42, 52). Based on the reported studies, the expected effect size for within-subjects and between-subjects differences was set at d=0.90. To have an 80% power to detect an effect size of d=0.90 with an alpha of 0.1 (since this is a pilot study), 15 participants are needed in each group. To account for loss to follow-up (estimated 10% dropouts rate), up to 16 participants will be recruited for each group, 48 patients total.

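### Sixteen recruited per arm less 10% dropout leaves 14.4 evaluable, not the required 15, and the 80% power claim is not tested against an average effect below d = 0.90

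*Combined protocol and SAP*

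**What the plan says.** The sample size paragraph (Section 12.0, Sample Size Justification) takes maximum phonation time (MPT) as its outcome. For the between-arm effect it uses a cross-sectional study of older people: "we compared MPT between the no-deficit group (complete glottal closure and normal spirometry) and the respiratory-deficit group", both with complete glottal closure. It reports no means or standard deviations from that contrast and concludes that "the expected difference between our control and experimental groups would represent a large effect size". It adds a within-subject effect above 1.2 from a study of young adult singers. It also gives the Aim 2 improvement thresholds: 4 s on MPT with SD 5.1, and 4 points on the Glottal Function Index (GFI) with SD 4.5. From these together, "the expected effect size for within-subjects and between-subjects differences was set at d=0.90".

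The calculation follows: "To have an 80% power to detect an effect size of d=0.90 with an alpha of 0.1", 15 participants per group are said to be needed. With an assumed 10% dropout, up to 16 per group are to be recruited, 48 in all.

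Three other places bear on this:

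- Section 10.0 stratifies on respiratory muscle pressure, and the first stratum is "1) within normal limits MIP and MEP". The entry criteria in Section 5.0 do not require a respiratory deficit.
- Section 1.0, Specific Aim 2, expects each training type to have its greatest effect in patients with the matching pressure deficit.
- The Data Analysis Plan in Section 12.0 specifies an intention-to-treat repeated measures model with two time points and three arms, and then Tukey's test to find which groups differ.

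**The concern.** There are two separate problems. First, the recruited number does not deliver the evaluable number on the plan's own dropout rate, and power is quoted with no reference to the test that will identify which arms differ. Second, the single value of 0.90 has to be the average over everyone in an arm. Part of its support is a contrast between people with and without a respiratory deficit, while the trial also enrols people whose muscle pressures are normal and predicts that response will vary with baseline pressure. Nothing shows what happens to power if the average is smaller.

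The stake is how a negative result is read. Section 1.0 says negative findings would show that respiratory function is not a viable target in these patients. Section 16.0 would treat a lack of sufficient improvement as grounds to abandon existing breathing exercises. A null result can carry that weight only if power was high across the effects that would matter.

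**Working it through.** **Inputs.** From the Sample Size Justification: d = 0.90, alpha 0.10 (sidedness not stated), 15 evaluable and up to 16 recruited per group, 10% dropout, MPT threshold 4 s with SD 5.1. From the Data Analysis Plan: three arms and Tukey comparisons.

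**Reproducing 15 per group.** Two groups, two-sided alpha 0.10, normal approximation: n = 2 x [(1.645 + 0.842)/0.90]^2 = 15.27. Power at 15 is 79.4%. Rounded up this is 16, so the plan's 15 reproduces within rounding. One-sided 0.10 would need 12 and two-sided 0.05 would need 20, so two-sided 0.10 is the reading that fits.

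**Dropout.** 16 x 0.90 = 14.4, below 15. For 15 evaluable, 15/0.90 = 16.7, so 17 would have to be recruited.

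**Power at d = 0.90.**

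- *Two-sample t.* Noncentrality is d x sqrt(n/2). At n = 15 it is 2.465 against a critical value of 1.701 (28 df): 77.6%. At n = 14 it is 2.381 against 1.706 (26 df): 75.0%. At 14.4: 76%. The exact t-test reaches 80% at 16 evaluable.
- *Three-arm F, means 0, 0.9, 0.9.* Noncentrality is n x 0.54, which is 8.10 at 15 and 7.56 at 14: 79.8% and 77.0% (78% at 14.4).
- *Tukey.* The critical value is q/sqrt(2) = 2.984/1.414 = 2.110 at n = 15 (42 df) and 2.114 at n = 14 (39 df). Power for at least one training arm against VFE was obtained by simulation with both training arms at d.

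**Power over a range of average d** (two-sided alpha 0.10, no baseline adjustment):

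| Test | n per arm | d = 0.90 | 0.78 | 0.675 | 0.45 |
|---|---|---|---|---|---|
| t-test | 15 | 77.6% | 67% | 56% | 33% |
| t-test | 14 | 75.0% | 65% | 54% | 32% |
| Tukey, one named arm v VFE | 15 | 64% | 52% | 40% | 20% |
| Tukey, one named arm v VFE | 14 | 61% | 49% | 38% | 19% |
| Tukey, at least one arm v VFE | 15 | 79% | 68% | 56% | 31% |
| Tukey, at least one arm v VFE | 14 | 76% | 65% | 53% | 29% |

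The value 0.78 is 4/5.1, the plan's own MPT threshold in SD units. The other two are illustrations of average d = 0.90 x [p + (1 - p) x r], where p is the share with a matched deficit and r is the effect in the rest relative to theirs. With p = 75% and r = 0, or p = 50% and r = 0.5, d = 0.675. With p = 50% and r = 0, d = 0.45. The documents give neither p nor r, so these are assumptions.

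**Reserve.** By the normal approximation, 80% power at 15 per arm needs d = (1.645 + 0.842) x sqrt(2/15) = 0.91. There is no margin for an average below 0.90.

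**The case against.** A reader might infer that the design cannot have 80% power, because 0.90 belongs to patients with a matched deficit and enrolling others must dilute it. The documents do not support that, for four reasons.

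- The plan sets 0.90 as the expected difference between arms, which is already an average. A larger effect in matched patients and a smaller one in the rest can average 0.90.
- Aim 2 says the effect will be greatest in matched patients, not confined to them.
- The reference contrast is spirometric, while the strata are defined by muscle pressure. The normal-pressure stratum is therefore not the source study's no-deficit group.
- The contrast is not the only source. The singers, who are not described as having a deficit, and the GFI threshold (4/4.5 = 0.89) also feed the choice.

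The use of reference groups with complete glottal closure is a stated modelling choice: voice therapy is taken to address the laryngeal deficit in every arm. The 4 s threshold is a within-person responder cut-off, so 0.78 serves here only as a plausible smaller effect and not as a between-arm target the plan has missed. The Tukey figure for one named arm is also the harsher of two readings, since the Aim 1 hypotheses accept either training type.

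Finally, a pre/post analysis may recover power. If d is on the raw scale and the pre/post correlation is 0.7 (an assumption), dividing d by sqrt(2 x (1 - 0.7)) for change scores or by sqrt(1 - 0.49) for baseline adjustment gives 75% or 81% at d = 0.675 and n = 15. At d = 0.45 the same calculation gives only 46% or 52%. With correlation 0.5, change scores gain nothing. The plan states neither the correlation nor the scale of d, so this gain cannot be credited or ruled out.

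These points stand, and they limit the second part of the concern to a missing justification. They do not touch the dropout arithmetic. The singers' figure is a within-subject change in young adults and gives little support to a between-arm difference.

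**Conclusion.** The point holds in a limited form. On the plan's own dropout rate, 16 recruited per arm falls short of 15 evaluable. Unadjusted power at d = 0.90 is then about 75-76% by t-test or 77-78% by the three-arm F, instead of 80%. That shortfall is small. The larger gap is for a named training arm under the planned Tukey test, at 61-64%; for at least one arm it is 76-79%.

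The stated power further depends on an average effect of about 0.90 over all enrolled participants. The plan does not justify that for a population with mixed respiratory function, and it gives no sensitivity analysis. How much power would be lost cannot be fixed from the documents, because stratum shares and stratum effects are absent. It should not be said that dilution has been shown, or that 0.90 applies only to matched-deficit patients. All figures assume two-sided alpha 0.10, equal arms and, unless noted, no gain from baseline measurements.

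**What to change.** Revise the Sample Size Justification in Section 12.0 without changing enrolment:

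1. Correct the dropout statement: 16 recruited per arm at 10% loss gives 14.4 evaluable.
2. Report power at 14 and 15 evaluable per arm under the planned analysis, including Tukey, separately for a named training arm and for at least one.
3. Show it for d = 0.90 and for a range of smaller average effects such as those tabulated above, labelling any dilution scenario as an assumption.
4. State whether alpha is two-sided, whether d is on the raw or change scale, and the pre/post correlation assumed.
5. In Sections 1.0 and 16.0, say that a null result at this power does not establish that respiratory training is ineffective.

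The cost is some rewriting and a slightly less favourable stated power. No extra participants are needed.

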Firstly, the medical chart of the participant will be reviewed to obtain the following information: height and weight. This information will be used to perform the respiratory and muscle pressure assessments. The medical chart will also be used to track the speech therapy appointments, since research visits will take place on the same days. Spirometry assessments will take place at baseline and after the fourth intervention session. Muscle pressure testing and acoustic assessments will be conducted at baseline and before and after each intervention session.

Spirometry: Prior to the tasks, the participant will put on a nose clip and make sure that the lips are well sealed around the tube with no air is escaping. They will be asked to breathe normally, and then take a full inspiration and blow out with force during at least 6 seconds, in the spirometer. Those maneuvers will be repeated at least three times, to verify test reliability. No more than eight repetitions should be needed(47). The participant is seated to reduce risks of fall.

• Muscle pressure (maximum inspiratory pressure-MIP- and maximum expiratory pressure-MEP):

- o MIP: the participant is instructed to exhale slowly and completely, seal lips firmly around the mouthpiece, and then breathe in forcefully. The PI will note the largest negative pressure sustained for at least one second on the pressure gauge. The participant will rest for about one minute and then repeat the maneuver up to 4 additional times (with the goal of matching the highest 2 trials within 10 cmH₂O)(48).
- o MEP: the participant is instructed to inhale slowly and completely, seal lips firmly around the mouthpiece, and then breathe out forcefully. The PI will note the largest positive pressure sustained for at least one second on the pressure gauge. The participant will rest for about one minute and then repeat the maneuver up to 4 additional times (with the goal of matching the highest 2 trials within 10 cmH₂O) (48).

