12.0 Data Management

Data Analysis Plan

Demographic characteristics will be compared across the 3 intervention groups, using a RxC contingency table method for categorical variables (gender, smoking history, voice use, racial and ethnic category) and a one-way ANOVA for continuous variables (age, weight, height). Baseline characteristics will be compared across the 3 intervention groups using a Kruskal-Wallis one-way analysis of variance by ranks for ordinal data (GFI, RSI, and VHI scores), a RxC contingency table for categorical variables (glottal gap shape, free edge contour, vertical level, phase closure) and a one-way ANOVA for continuous variables. Aim 1: To assess the effects of respiratory training on voice and respiratory outcomes in patients with presbyphonia. Data will be analyzed on an intention-to-treat basis using multifactor repeated measures generalized linear regression. Distributional assessment will be made for each outcome to confirm optimal distributional assignment and potential need for outcome transformation (i.e. log link). In the model, the repeated factor is time, which has two levels (pre- or post-intervention) and the independent factor is the intervention, which has three levels (IMST, EMST, VFE). In the case of a significant between-subjects effect, multiple comparison tests will be conducted to determine which groups differ. The post-hoc analysis will be done using Tukey's honestly significant difference (offering protection against type I error without being too conservative). Spearman and Person correlations will be calculated to establish inter and intrarater reliability. Aim 2: To identify profiles of presbyphonic patients that would benefit the most from respiratory training. Logistic regression will be conducted to predict which patients improved following inspiratory training and which patients improved following expiratory training, based on their baseline clinical characteristics. Two outcome variables will be indicative of meaningful clinical improvement: 1) MPT (to measure function), and 2) GFI (to measure patient perception of function). Meaningful clinical improvement will be defined by an increase of at least 4 seconds in MPT or a decrease of at least 4 points in GFI score. Participants will be dichotomized as having meaningful clinical improvement, or not, based on these outcomes. Predictors will include MIP, MEP, maximum SPL, breaths per minute, FVC, FEV1, and P_s. These measures were chosen because they are directly influenced by the integrity of the respiratory system.

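### Sixteen per arm does not cover the stated 10% dropout (17 are needed), and the gate before Tukey should name the group-by-time effect

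*Combined protocol and SAP*

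**What the plan says.** All of the statistical text is in the combined protocol and SAP, section 12.0.

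- **Sample Size Justification, effect size.** Maximum phonation time (MPT) is the sizing outcome, and "the expected effect size for within-subjects and between-subjects differences was set at d=0.90". The between-group value comes from a published cross-sectional comparison in older people: "we compared MPT between the no-deficit group (complete glottal closure and normal spirometry) and the respiratory-deficit group".
- **Sample Size Justification, power and dropout.** The power statement reads "80% power to detect an effect size of d=0.90 with an alpha of 0.1 (since this is a pilot study), 15 participants are needed", a figure that applies per arm. The dropout allowance is then given as: "To account for loss to follow-up (estimated 10% dropouts rate), up to 16 participants will be recruited for each group, 48 patients total". The test, its sidedness and the standard deviation behind d (raw MPT or pre-to-post change) are not stated.
- **Data Analysis Plan, Aim 1.** In the repeated-measures model, "the repeated factor is time, which has two levels (pre- or post-intervention) and the independent factor is the intervention, which has three levels". The gate is: "In the case of a significant between-subjects effect, multiple comparison tests will be conducted to determine which groups differ". The pairwise step follows: "The post-hoc analysis will be done using Tukey's honestly significant difference". No family-wise alpha is given for it.

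The hypotheses in section 1.0 are about greater improvement in the inspiratory and/or expiratory training groups than in the voice-exercise (VFE) group.

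**The concern.** Three things do not line up.

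1. The dropout allowance is presented as covering 10% loss, and by the plan's own numbers it does not.
2. The gate is worded as a between-subjects effect. In a model with a within-person time factor, that ordinarily means the group main effect averaged over pre and post. The hypothesis is about the group difference in change, which is the group-by-time effect, and the plan never names that term.
3. The one power figure in the plan is not attached to any planned test, whereas the decision about which groups differ is left to Tukey.

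At stake is how a null result is read. Section 1.0 says negative findings would show that respiratory function is not a viable target; section 16.0 says only that they would raise questions. Either reading needs the power of the deciding test on record, and needs that test to address improvement.

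**Working it through.** **Inputs from section 12.0:** d = 0.90, alpha = 0.10, power 80%, 15 completers per group, 10% dropout, 16 recruited per group (48), three groups.

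**Assumptions, not in the documents:** two-sided testing; family-wise alpha 0.10 for Tukey (0.05 also shown); pre/post correlation ρ of 0.3, 0.5 or 0.7; equal baselines.

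**1. Reproducing the 15.** Normal approximation, one pair: n = 2(1.645 + 0.842)²/0.90² = 12.37/0.81 = 15.3. Exact two-sample t at n = 15: noncentrality 0.90·√(15/2) = 2.465, critical value 1.701 (28 df), power 77.6%. Three-group F with both training arms 0.90 above VFE: noncentrality 15·(2/3)·0.81 = 8.10, critical value 2.434 (2, 42 df), power 79.8%; the result is the same if only one arm gains 0.90. So 15 roughly fits an unadjusted two-sided pair or the omnibus F. One-sided testing fits less well: the normal approximation then needs 12 per arm, and t power at 15 would be 87.4%.

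**2. Dropout.**
- Needed: 15/(1 − 0.10) = 16.7, so 17 per arm and 51 in total. The cruder 15 × 1.1 = 16.5 also rounds up to 17.
- Loss that 16 can absorb: 1/16 = 6.25%.
- Expected completers: 16 × 0.9 = 14.4 per arm; 48 × 0.9 = 43.2 against 45.

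Power with d = 0.90 on the analysed scale:

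| Completers per arm | Unadjusted t | Three-group F | One named Tukey pair, 0.10 |
|---|---|---|---|
| 14 | 75.0% | 77.0% | 60.8% |
| 14.4 | 76.1% | 78.1% | 62.1% |
| 15 | 77.6% | 79.8% | 64.0% |
| 16 | 80.0% | 82.3% | 67.0% |

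The loss due to dropout is the step from 15 to 14.4: 1.5 points (t) or 1.7 points (F).

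**3. The gate run as a main effect.** Suppose training raises post MPT by 0.90 raw SD and baselines are equal. The group difference in the pre/post average is 0.90/2 = 0.45 SD. The SD of that average is √((1+ρ)/2), so d′ = 0.45/√((1+ρ)/2).

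| ρ (assumed) | d′ | F power, 15 per arm | F power, 14 per arm |
|---|---|---|---|
| 0.3 | 0.558 | 43.8% | 41.6% |
| 0.5 | 0.520 | 39.6% | 37.7% |
| 0.7 | 0.488 | 36.3% | 34.5% |

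If d = 0.90 is on change instead, d′ = 0.90·√((1−ρ)/(1+ρ)) = 0.660, 0.520, 0.378, and gate power at 14 per arm is 52.7%, 37.7%, 24.8%.

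**4. The Tukey step.** The critical value is the studentized range quantile over √2, which is 2.110 at 15 per arm and family-wise 0.10. That gives the last column of the first table. At family-wise 0.05 a named pair has 51.9% at 15 and 48.5% at 14. With the omnibus gate on the analysed scale (simulation, 200,000 runs), at least one training arm beats VFE in about 78% (15 per arm) or 75% (14 per arm) of trials if both truly gain 0.90.

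If d = 0.90 is on raw MPT and change is analysed, d′ = 0.90/√(2(1−ρ)) = 0.761, 0.900, 1.162 for the three correlations. The named pair then has 49%, 64%, 85% at 15 per arm and 47%, 61%, 83% at 14. At 15 per arm it reaches about 80% near ρ = 0.65.

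**The case against.** The strongest reply is that this is a pilot with a relaxed alpha, short by one participant per arm. That stands as to size: the dropout slip costs less than two points. A reader might infer that dropout alone takes power from 80% to 76%. It does not; most of that gap is the exact t test (77.6% at 15) against the stated 80%.

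The analysed number may also exceed 14.4. The analysis is by intention to treat, and "Muscle pressure testing and acoustic assessments will be conducted at baseline and before and after each intervention session", with the section 10.0 acoustic protocol including the longest sustained vowel. If all 16 per arm had a usable post value, power would be 80.0% (t) or 82.3% (F). The plan does not say that session values stand in for a missing final one, so this softens the point without removing it.

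Sizing a pilot on an unadjusted pair or the omnibus test is an ordinary choice, and the hypothesis is met if either arm is better. On that criterion Tukey comes close to 80% when both arms work. A reader might infer that the Tukey step is definitely underpowered. The documents do not support that, because they give neither the scale of d, nor the correlation, nor the family-wise alpha. The derivation from MPT values and pooled standard deviations leans towards raw MPT, where a high correlation would bring a named pair above 80%.

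Finally, the improvement wording in section 1.0 suggests that the investigators intend the change comparison. That is plausible, and it is why the main-effect gate is a reading to be closed off, not an established error in intent.

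**Conclusion.** The dropout step is wrong on the plan's own figures: 17 per arm (51) are needed, and 16 per arm (48) is expected to leave about 43 completers. Its effect on power is small, 1.5 to 1.7 points under two-sided alpha 0.10 and d = 0.90 on the analysed scale.

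The gate wording has the larger consequence. Run as a group main effect, it does not test greater improvement, and a training with the assumed raw effect would open the Tukey step less than half the time (about 44% to 36% at 15 per arm for assumed correlations 0.3 to 0.7).

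The 80% describes an unadjusted pair or the omnibus F. It does not describe one named Tukey pair if d is on the analysed scale: about 64% at 15 and 61% at 14 per arm at family-wise 0.10, or about 52% and 48.5% at 0.05. This third part is conditional on quantities that the plan leaves open. None of it shows that the trial must recruit more. It should be fixed in the text.

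**What to change.** 1. In section 12.0, Sample Size Justification, replace the dropout sentence with:

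> With 16 recruited per group and 10% loss, about 43 of 48 participants (14 to 15 per group) are expected to complete. At two-sided alpha 0.10 and d=0.90 on pre-to-post MPT change, power is about 77-78% for the omnibus test of group differences in change, about 75% to show at least one training arm better than VFE by Tukey if both have this effect, and about 61% for one named pair (14 per group, family-wise alpha 0.10).

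The sponsor should confirm the three assumptions in it: two-sided testing, d on change, and the Tukey alpha. If raw MPT was intended, the figures should be recomputed with a justified pre/post correlation.

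2. In section 12.0, Data Analysis Plan, Aim 1, replace the between-subjects effect in the gate with:

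> group-by-time effect (group difference in pre-to-post change)

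**Cost.** A replaced sentence and a replaced phrase, with no change to enrolment, visits or comparisons. The stated power becomes slightly less favourable. Recruiting 17 per arm would be the alternative, and the plan's accrual projection of 64 exceeds 51, but the gain is too small to require it.
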